1.2 SCHEMA

Figure 1 - Graphical study design

LPS15991

AD Atopic dermatitis
 HV Healthy volunteers
 W Week
 BL Baseline
 EoT End of Treatment
 EoS End of Study

Dupilumab in AD patients: D1 (V02,W0) baseline
 D15±2days (V06, W2)
 D29±2days (V08, W4),
 D43±2days (V09, W6),
 D57±3days (V10, W8)
 D71±3days (W10 Dupilumab at home)
 D85±3days V11, W12)
 D99±3days (W14, Dupilumab at home)

1.3 SCHEDULE OF ACTIVITIES (SOA) / AD PATIENTS

Phase	Screening	Baseline	Treatment Phase										EoT	EoS ^a	Un-scheduled Visit	Premature EoT
Day	D-28 to D-1	D 1	D4 ±2 days	D8 ±2 days	D11 ±2 days	D15 ±2 days	D22 ±2 days	D29 ±2 days	D43 ±2 days	D57 ±3 days	D85 ±3 days	D113 ±3 days	D141 ±3 days	UNSCH		
Week		W0		W1		W2	W3	W4	W6	W8	W12	W16	W20			
Visits	V01	V02	V03	V04	V05	V06	V07	V08	V09	V10	V11	V12	V13			
Informed consent / assent form	X															
Inclusion/exclusion criteria	X	X														
Medical/surgical history / IGA / Demographics	X															
Prior/concomitant medications / procedures	X	X	X	X	X	X	X	X	X	X	X	X	X	X	X	
Confirm emollient and washing compliance ^j	X	X	X	X	X	X	X	X	X	X	X	X		X	X	
Study treatment administration																
SC administration of dupilumab ^b		X				X		X	X	X	X			(X)		
Study drug self-administration training by site staff ^o										X				(X)		
Study drug will be handed out at V10 (Week 8) for self-administration at Week 10 and at V11 (Week 12) for self-administration at Week 14										X	X			(X)		
Compliance check of self-administered study drug at Week 10 and Week 14											X	X		(X)	X	

Phase	Screening	Baseline	Treatment Phase										EoT	EoS ^a	Un-scheduled Visit	Premature EoT
Day	D-28 to D-1	D 1	D4 ±2 days	D8 ±2 days	D11 ±2 days	D15 ±2 days	D22 ±2 days	D29 ±2 days	D43 ±2 days	D57 ±3 days	D85 ±3 days	D113 ±3 days	D141 ±3 days	UNSCH		
Week		W0			W1		W2	W3	W4	W6	W8	W12	W16	W20		
Visits	V01	V02	V03	V04	V05	V06	V07	V08	V09	V10	V11	V12	V13			
Skin barrier function test in lesional and non-lesional skin^c																
TEWL at baseline/ before STS ^{l,m}		X	X	X	X	X	X	X	X	X	X	X	X		(X)	X
TEWL after STS assessment ^h		X ⁱ				X ⁱ		X ⁱ		X ⁱ	X ⁱ	X ⁱ			(X) ⁿ	X ⁿ
Lipidomics, filaggrin (FLG) breakdown products, proteomics, and transcriptomics assessment from skin tape strip ⁱ		X ⁱ				X ⁱ		X ⁱ		X ⁱ	X ⁱ	X ⁱ			(X) ⁿ	X ⁿ
Standardized photographs of lesional and non-lesional skin areas used for TEWL ^l		X	X	X	X	X	X	X	X	X	X	X			(X)	X
Standardized full body photographs		X	X	X	X	X	X	X	X	X	X	X			(X)	X
EASI	X	X	X	X	X	X	X	X	X	X	X	X			(X)	X
ISS on lesion erythema and edema/papulation	X	X	X	X	X	X	X	X	X	X	X	X			(X)	X
SCORAD	X	X	X	X	X	X	X	X	X	X	X	X			(X)	X
Patient reported outcomes (PRO)																
POEM		X		X		X	X	X	X	X	X	X			(X)	X
DLQI/CDLQI ^f		X		X		X	X	X	X	X	X	X			(X)	X
Peak pruritus NRS ^g		X	X	X	X	X	X	X	X	X	X	X			(X)	X

Phase	Screening	Baseline	Treatment Phase									EoT	EoS ^a	Un-scheduled Visit	Premature EoT
			D4 ±2 days	D8 ±2 days	D11 ±2 days	D15 ±2 days	D22 ±2 days	D29 ±2 days	D43 ±2 days	D57 ±3 days	D85 ±3 days				
Day	D-28 to D-1	D 1												UNSCH	
Week		W0	W1			W2	W3	W4	W6	W8	W12	W16	W20		
Visits	V01	V02	V03	V04	V05	V06	V07	V08	V09	V10	V11	V12	V13		
Quality of sleep NRS ^g		X	X	X	X	X	X	X	X	X	X	X		(X)	X
Safety															
Adverse event collection	X	X	X	X	X	X	X	X	X	X	X	X	X	X	X
Height		X													
Body weight		X										X			X
Vital signs ^d	X	X								X		X		(X)	X
Physical examination	X	X ^k										X ^k			X ^k
Pregnancy test (urine), WOCBP only ^e	X	X						X		X	X	X			
DNA sampling for filaggrin gene sequencing		X													
Optional assessments															
DNA sampling for future research		X													
Biomarker research samples (serum and plasma)		X										X			X

a EoS safety follow-up by phone.

b Loading dose dupilumab arm 600 mg (300 mg x 2 ie, two 300 mg syringes) for all adult patients and for those adolescents weighing 60 kg and above, and 400 mg (200 mg x 2 ie. two 200 mg syringes) for adolescent patients below 60 kg, followed by bi-weekly SC dosing of 300 mg dupilumab to adults and adolescents weighing 60 kg and above and bi-weekly SC dosing of 200 mg to adolescents weighing below 60 kg. Dupilumab administration on following days: D1 (V02,W0) baseline, D15±2days (V06, W2), D29±2days (V08, W4), D43±2days (V09, W6), D57±3days (V10, W8), D71±3days (W10; self-administration of dupilumab at home), D85±3days V11, W12), D99±3days (W14; self-administration of dupilumab at home).

c Assessments on treatment days are to be conducted before administration of dupilumab.

d Vital signs, including systolic and diastolic blood pressure (mmHg), pulse rate (beats per minute), body temperature (°C), and respiratory rate will be measured at Screening, Baseline at Week 0, Week 8, and Week 16 (EoT). Height (cm) will be measured at Baseline only. Body weight (kg) will be measured at Baseline, and Week 16 (EoT).

e Only for women of childbearing potential. Pregnancy will lead to definitive treatment discontinuation in all cases.

f DLQI will be used for adults; CDLQI will be used for adolescents.

- g* Peak pruritus NRS and quality of sleep NRS will be assessed daily from Day-7 to Day -1; daily from Day 1 to Day 29 and then for the 7 days prior to Week 6, Week 8, to Week 12 and to Week 16 by e-diary. Patients will bring the eDiary to the site at each visit. eDiary will be reviewed for any questionnaires omission and dispensed back to patients at each visit.
- h* TEWL to be conducted before STS and then after 5, 10, 15, and 20 STS in pre-defined lesional and non-lesional skin. All skin tape strips will be collected and stored.
- i* At Week 0, 8 and 16 STS will be conducted on the first spot within the predefined skin area. At Week 2 STS will be conducted on the second spot within the predefined skin area. At Week 4 and 12 STS will be conducted on the third spot within the predefined skin area. TEWL will be assessed in lesional and non-lesional skin before STS and after 5, 10, 15, and 20 STS. All skin tape strips will be collected and stored for lipidomics, proteomics, and transcriptomics analyses.
- j* Emollients should NOT be applied from Day -7 to the EoT (Week 16, Day 113) to the targeted, pre-defined skin areas that will be used for TEWL assessment. Participants should not take showers or soaking in a bathtub within 6 hours before TEWL assessment. Compliance must be documented in participant's source data. Emollients for use during the study will be provided by the study site to study participants. Use of emollients should be documented in a diary.
- k* Limited to skin-related physical examination at baseline and EoT visit.
- l* Pre-defined lesional (3 spots) and non-lesional skin areas (3 spots), whereby the assessment spots on non-lesional skin are located about 4 cm apart from the edge of the AD lesion.
- m* TEWL will be measured at each of the three closely adjacent spots within the predefined skin areas at all visits as baseline assessment; if there is STS, subsequent TEWL assessment will only be done at the lesional and no-lesional spot, at which STS is performed.
- n* In case STS assessment is to be conducted at an unscheduled visit or at a premature end of treatment visit the assessment should be conducted at that spot of the skin area, for which the period passed since the last STS assessment is the longest.
- o* Study participants may be trained for study drug self-administration starting from D1 (Visit 2). Training should be completed and documented at Week 8 (Visit 10). Site staff has to verify patients' injection technique before they are allowed to self-inject at home. On-site injections may be performed by either site staff or AD patient or caregiver/parent/legal representative if previously trained on self-injection technique

EASI = Eczema Area and Severity Index; EoT = End of Treatment Phase; EoS = End of Study; IGA = Investigator Global Assessment; SCORAD = SCORing Atopic Dermatitis; STS = Skin Tape Stripping;
TEWL = Transepidermal Water Loss; V = Visit; W = Week; WOCBP = Women of Childbearing Potential

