a Subcutaneous injection sites should alternate between the upper thighs, 4 quadrants of the abdomen or the upper arms, so that the same site is not injected twice during consecutive administrations. Injection in the upper arms can only be done by a trained person (parent/legally authorized representative/caregiver trained by Investigator or Delegate) or health care professional but not the participant themselves.

IMP: investigational medicinal product

Investigational medicinal product(s)

When the participant has a study visit, the IMP will be administered following clinical procedures and blood collection (if any). AD patients will be monitored for at least 30 minutes after each injection. Patients should monitor themselves for at least 30 minutes after performing self-injection at home.

Study participants may be trained for study drug self-administration starting from D1 (Visit 2). Training should be completed and documented at Week 8 (Visit 10). Site staff has to verify patients injection technique before they are allowed to self-inject at home. On-site injections may be performed by either site staff or AD patient or caregiver/parent/legal representative if previously trained on self-injection technique.

Between the protocol-scheduled on-site visits, participants are allowed to self-inject IMP at home. Patient should also be trained by the site staff to recognize potential signs and symptoms of hypersensitivity reaction in order to self-monitor at home. In case of hypersensitivity symptoms the patient should contact healthcare provider/emergency. The training must be documented in the participant's study file. Participants will be dispensed an adequate amount of IMP for home administration to last through the next scheduled study visit. Participants who prefer to have a healthcare professional administer the IMP may choose to have injections administered at the study site.

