7 DISCONTINUATION OF STUDY INTERVENTION AND PARTICIPANT DISCONTINUATION/WITHDRAWAL

7.1 DISCONTINUATION OF STUDY INTERVENTION

7.1.1 Definitive discontinuation

In rare instances, it may be necessary for a participant to permanently discontinue (definitive discontinuation) study intervention. If study intervention is definitively discontinued, the participant will remain in the study to be evaluated for TEWL, lipidomics, proteomics and transcriptomics. See the SoA for data to be collected at the time of discontinuation of study intervention and follow-up and for any further evaluations that need to be completed.

Pregnancy in a female participant will lead to definitive intervention discontinuation in all cases.

Handling of participants after definitive intervention discontinuation

Participants will be followed-up according to the study procedures specified in this protocol up to the scheduled date of study completion, or up to recovery or stabilization of any AE to be followed-up as specified in this protocol, whichever comes last.

If possible, and after the definitive discontinuation of intervention, the participants will be assessed using the procedure normally planned for the last dosing day with the IMP.

All cases of definitive intervention discontinuation must be recorded by the Investigator in the appropriate pages of the e-CRF when considered as confirmed.

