7.2 PARTICIPANT DISCONTINUATION/WITHDRAWAL FROM THE STUDY

- A participant may withdraw from the study at any time at his/her own request, or may be withdrawn at any time at the discretion of the Investigator for safety, behavioral, compliance, or administrative reasons. This is expected to be uncommon.
- At the time of discontinuing from the study, if possible, an early discontinuation visit should be conducted, as shown in the SoA. See SoA for data to be collected at the time of

study discontinuation and follow-up and for any further evaluations that need to be completed.

- The participant will be permanently discontinued both from the study intervention and from the study at that time.
- If the participant withdraws consent for disclosure of future information, the Sponsor may retain and continue to use any data collected before such a withdrawal of consent.
- If a participant withdraws from the study, he/she may request destruction of any samples taken and not tested, and the Investigator must document this in the site study records.

If participants no longer wish to take the IMP, they will be encouraged to remain in the study.

The Investigators should discuss with them key visits to attend. The value of all their study data collected during their continued involvement will be emphasized as important to the public health value of the study.

Participants who withdraw from the study intervention should be explicitly asked about the contribution of possible AEs to their decision, and any AE information elicited must be documented.

All study withdrawals should be recorded by the Investigator in the appropriate screens of the e-CRF and in the participant's medical records. In the medical record, at least the date of the withdrawal and the reason should be documented.

In addition, a participant may withdraw his/her consent to stop participating in the study. Withdrawal of consent for intervention should be distinguished from withdrawal of consent for follow-up visits and from withdrawal of consent for non-participant contact follow-up, eg, medical record checks. The site should document any case of withdrawal of consent.

Participants who have withdrawn from the study cannot be reallocated (treated) in the study. Their inclusion and intervention numbers must not be reused.

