8.4.5 Pregnancy

- Details of all pregnancies in female participants will be collected after the start of study intervention and until 12 weeks after EoS.
- If a pregnancy is reported, the Investigator should inform the Sponsor within 24 hours of learning of the pregnancy and should follow the procedures outlined in Appendix 4 ([Section 10.4](#)).
- Abnormal pregnancy outcomes (eg, spontaneous abortion, fetal death, stillbirth, congenital anomalies, ectopic pregnancy) are considered SAEs.

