- The Investigator will collect pregnancy information on any female participant who becomes pregnant while participating in this study. The initial information will be recorded on the appropriate form and submitted to the Sponsor within 24 hours of learning of a participant's pregnancy.
- The participant will be followed to determine the outcome of the pregnancy. The Investigator will collect follow-up information on the participant and the neonate and the information will be forwarded to the Sponsor. Generally, follow-up will not be required for longer than 6 to 8 weeks beyond the estimated delivery date. Any termination of pregnancy will be reported, regardless of fetal status (presence or absence of anomalies) or indication for the procedure.
- Any pregnancy complication or elective termination of a pregnancy for medical reasons will be reported as an AE or SAE.
- A spontaneous abortion (occurring at <22 weeks gestational age) or still birth (occurring at >22 weeks gestational age) is always considered to be an SAE and will be reported as such.
- Any post-study pregnancy related SAE considered reasonably related to the study intervention by the Investigator will be reported to the Sponsor as described in [Section 8.4.4](#). While the Investigator is not obligated to actively seek this information in former study participants, he or she may learn of an SAE through spontaneous reporting.
- Any female participant who becomes pregnant while participating in the study will discontinue study intervention.

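### Section 1.3 repeats every Week 16 assessment at Premature EoT except the urine pregnancy test, and no other text requires that test when a treated woman withdraws

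*Protocol*

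**What the plan says.** **Schedule.** In Protocol Section 1.3 the row "Pregnancy test (urine), WOCBP only" is marked at screening, Day 1 and Weeks 4, 8, 12 and 16. It is blank at EoS, Unscheduled and Premature EoT. Section 8.3.3 ties urine pregnancy testing to the schedule and adds no rule of its own.

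**Withdrawal from the study.** Section 7.2 says that, where possible, "an early discontinuation visit should be conducted, as shown in the SoA". The participant is then out of both treatment and study.

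**Stopping drug only.** Section 7.1.1 keeps these patients in the study: "Participants will be followed-up according to the study procedures specified in this protocol up to the scheduled date of study completion". It adds that, where possible after definitive discontinuation, "the participants will be assessed using the procedure normally planned for the last dosing day with the IMP". It names no pregnancy test.

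**Discretionary testing.** Table 5 in Appendix 2 lists the urine hCG test for women of childbearing potential on an as-needed basis.

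**Reporting.** Section 8.4.5 sets the collection window: "Details of all pregnancies in female participants will be collected after the start of study intervention and until 12 weeks after EoS". Sections 7.1.1 and 8.4.8 make pregnancy a reason to stop dupilumab, require a report to the sponsor within 24 hours and follow-up to outcome, and class abnormal outcomes as SAEs. The SAP adds nothing on pregnancy testing.

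**The concern.** The duties to report and follow a pregnancy depend on someone detecting it. For a woman who withdraws, the premature EoT visit may be the site's last chance to test after exposure. The schedule has her weight, vital signs and even optional biomarker blood taken at that visit, but not the inexpensive test the trial already uses at Week 16. An early pregnancy exposed to dupilumab could then go unrecognised by the site when she leaves. What is at stake is safety information on a few participants at most.

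**Working it through.** **1. Row count in Section 1.3.** The rows marked at Week 16 are:

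- medications, emollient and washing check, compliance check (3)
- TEWL before STS, TEWL after STS, omics from strips (3)
- photographs of the assessed areas, full-body photographs (2)
- EASI, ISS, SCORAD (3)
- POEM, DLQI/CDLQI, peak pruritus NRS, sleep NRS (4)
- adverse events, body weight, vital signs, physical examination (4)
- urine pregnancy test (1)
- optional serum and plasma samples (1)

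Total: 3 + 3 + 2 + 3 + 4 + 4 + 1 + 1 = 21. Marked at Premature EoT: 20. The only one missing is the pregnancy test.

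**2. Is the blank real?** The pregnancy row reads as 15 cells (V01 to V13, Unscheduled, Premature EoT), with marks at V01, V02, V08, V10, V11 and V12. Body weight and vital signs, in the same part of the table, also read as 15 cells and do carry the Premature EoT mark, so the columns have not shifted. The separate healthy-volunteer table in Section 1.4 has the same blank. A cell lost in text extraction is therefore unlikely.

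**3. Does other text supply the test?**

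| Text | Effect at early exit |
|---|---|
| 8.3.3 | Refers back to the schedule |
| 7.2 | Refers back to the schedule |
| 7.1.1, last dosing day | Applies only where possible and names no test. The planned last dose (Week 14) is taken at home with no test; the last planned on-site dose (Week 12) has one. The text does not say which is meant |
| Table 5 | Permits a test, does not require it |

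**4. How old can the last test be?** Tests from baseline fall on Days 1, 29, 57, 85 and 113. Doses fall on Days 1, 15, 29, 43, 57, 71, 85 and 99. Section 6.1 puts on-site dosing after the visit's procedures, so a dose on a test day follows the test. Visit windows are ±2 days at Day 29 and ±3 days at Days 57, 85 and 113.

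| Interval between tests | Nominal gap (days) | Longest gap within windows (days) | Doses since the earlier test |
|---|---|---|---|
| Day 1 to 29 | 29 − 1 = 28 | 31 − 1 = 30 | Days 1, 15: 2 |
| Day 29 to 57 | 57 − 29 = 28 | 60 − 27 = 33 | Days 29, 43: 2 |
| Day 57 to 85 | 85 − 57 = 28 | 88 − 54 = 34 | Days 57, 71: 2 |
| Day 85 to 113 | 113 − 85 = 28 | 116 − 82 = 34 | Days 85, 99: 2 |

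A woman who withdraws just before her next test is due is thus up to 28 days (nominal), or 30 to 34 days at the window limits, and up to two doses past her last one. A missed visit would lengthen this.

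**5. How many women?** Section 9.2 allows 15% drop-out: 0.15 × 24 = 3.6, and 24 − 20 = 4. That allowance covers both sexes and is framed around evaluability, so it also includes people who do not withdraw. The number of women of childbearing potential is not given. The number affected could be zero.

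**6. Does the 8.4.5 window fail for an early leaver?** Take withdrawal on Day 50 with last dose on Day 43; 12 weeks = 84 days.

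- EoS read as the exit visit: 50 + 84 = Day 134
- EoS read as a call 4 weeks after exit: 50 + 28 + 84 = Day 162
- EoS read as the scheduled Day 141: 141 + 84 = Day 225
- Contraception period in E 18 (12 weeks after last dose): 43 + 84 = Day 127

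The readings differ by up to 225 − 134 = 91 days, but all of them outlast the contraception period. Because exit falls on or after the last dose, that is true in general.

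**The case against.** The best defence is that the blank is a missing requirement, not a barrier. Table 5 lets the investigator test at exit, adverse events are collected at that visit, and 7.1.1 can be read as calling for the Week 12 procedures, which include a test. All of that stands, and it keeps the point small. It does not close the gap, because none of these provisions obliges the site to test.

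Three stronger readings are tempting and should not be made.

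- A reader might infer from "The Investigator will collect pregnancy information on any female participant who becomes pregnant while participating in this study" that Appendix 4 ignores later pregnancies. It does not: the same appendix requires reporting of post-study pregnancy-related SAEs that the investigator considers reasonably related to treatment. Section 8.4.8 requires 24-hour reporting and follow-up to outcome without limiting this to the period of participation.
- A reader might infer that early leavers have no workable collection window. The end date is unclear, but Section 7.2 naturally suggests withdrawal plus 12 weeks, and no reading set out above falls short of the contraception period.
- A reader might see a surveillance failure in the lack of scheduled contact between the Week 20 contact ("EoS safety follow-up by phone") and the end of the 8.4.5 window. That section sets a period for collecting reports and promises no further visits. Whether women are told to report later pregnancies may be settled in the consent form or study reference manual, which cannot be seen here.

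**Conclusion.** The point holds, narrowly. One assessment out of 21 is not carried over from Week 16 to Premature EoT, and no other provision makes it mandatory there. It concerns only treated women of childbearing potential who withdraw from the study; healthy volunteers share the blank but receive no drug. The conclusion assumes that the schedule governs what is done at the exit visit, as 7.2 and 8.3.3 say, and that the study reference manual does not already add an exit test. It is a minor safety improvement. TEWL and all other efficacy results are unaffected. Confidence is high for the blank cell. The wording of 8.4.5 is a side issue on which the point does not depend.

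**What to change.** In Section 1.3, mark the urine pregnancy test (women of childbearing potential) under Premature EoT. This costs one urine test, of a kind already used in the trial, for each such woman who leaves early, at a visit that 7.2 already asks for. It helps only if that visit takes place. No analysis changes and the Week 16 data lock is not delayed.

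Optional clarification: state in 8.4.5 that for a woman who leaves before EoS the collection window ends 12 weeks after her premature EoT visit, or 12 weeks after the withdrawal date if no visit is held. This keeps the 12 weeks already chosen and cannot end before the E 18 contraception period. It costs one sentence.
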